NCT02228499

Title: Academic Achievement in Children with Asthma

Date: June 22, 2018

Academic Achievement in Children with Asthma

Abstract

Background: Asthma is the most common chronic disease of childhood with a prevalence that is 1.6 times greater in African American (AA) children than in Non-Hispanic White children.¹ Nationally, 700,000 children are seen for asthma in Emergency Departments (ED) every year, 1% of which are seen at Children's National Health System (CN) in Washington, DC. School performance and school attendance has not been well studied in urban children with asthma, especially at the middle school level.

Objective: Our purpose is to test the hypothesis that children with asthma have worse school performance than middle school children without asthma in Washington DC public schools.

Methods: We will conduct a cross-sectional observational study of children in 3rd-8th grade in the 2015-2016 academic year with and without asthma recruited from the Emergency Departments and the IMPACT DC asthma clinic at CN. We will collect demographic information, asthma severity information (for cases), and request that parents mail report cards and standardized test scores directly to the investigators. We will use multivariable linear and logistic regression to determine if the presence of asthma is associated with school performance.

Research Plan

A. Background and Specific Aims

Asthma is the most common chronic disease of childhood with a prevalence that is 1.6 times greater in African American (AA) children than in Non-Hispanic White children.¹ Nationally, 700,000 children are seen for asthma in Emergency Departments (ED) every year, 1% of which are seen at Children's National Medical Center (CN) in Washington, DC. The asthma prevalence rate among African America (AA) children and teens in Washington, DC is 20% higher than the national rate² and overall ED utilization rates for asthma are 4.3 times the national rate.³ In 2007, approximately 10.5 million school days were lost due to asthma.¹

Asthma severity may impact academic performance due to increased absenteeism. A study of Canadian school children showed that children with the most severe asthma had the lowest math and reading scores.⁴ Tsakiris also showed that children with asthma on inhaled corticosteroids had better academic achievement than children with asthma not on long-term controller therapy, suggesting that poor control is associated with worse school performance.⁵

However, academic performance is dependent on many other factors, such as socio-economic status of the local district and resources available. Availability of skilled nursing differs between schools, impacting children with asthma; Hillemeier's study of children with asthma in Pennsylvania schools showed that less than half of secondary schools had adequate school nurse coverage, and that this reduced services provided to children with asthma.⁶ Children whose asthma is not managed at school may be absent more often. Parental education also plays a part in a child's school performance. Tsakiris et al, showed that in Greece, lower parental education level was independently associated with poor school performance in children with asthma.⁵

Early adolescence (ages 10-13) is identified as a time of great transition with both developmental and biologic changes; in this time period male children with asthma generally improve and female with asthma develop worsening asthma, likely due to hormone effects. It has been shown that programs to reduce asthma symptoms in both younger children (elementary school) and older children (high school) do not work well in early adolescent children (middle school).⁷

In addition, despite the National Asthma Education Prevention Program (NAEPP, 2007) guidelines that encourage the assessment of the quality of life (QOL) in children, there has been minimal research on QOL in children with asthma.

Given the scarcity of information on the association between pediatric asthma and academic achievement, school attendance, and the QOL, and the need to establish baselines within individual communities, we have designed a study to examine the association between asthma in children in grades 3-8 and academic achievement, school attendance, and the QOL. ***Our overall hypothesis is that children with asthma will have worse school performance compared to children without asthma.***

Specific Aim 1: To determine the association between asthma and school performance by comparing grade point averages (GPA) in children from 3rd-8th grade with and without asthma. We will enroll an additional 60 children in grades 3-8 with asthma (cases) from the ED/IMPACT DC and compare them with a group of 60 children in grades 3-8 without asthma (controls) recruited from the ED. Report cards will be collected between May 2016-November 2016 or until 60 cases and 60 controls have been recruited, and GPAs will be compared. We expect children with asthma will have lower GPAs .

B.**Significance:**

School achievement in elementary and middle school students with asthma is not well understood; this study will be pivotal in identifying if middle school students with asthma in the Washington DC are performing more poorly than their non-asthmatic counterparts.

C. Preliminary studies

We have not previously studied academic success in children with asthma.

D. Research Design and Methods

We are proposing a cross-sectional case-control observational study of children in grades 3-8 to compare academic achievement and school attendance between children with and without asthma. 60 children with asthma (cases) will be recruited from the IMPACT DC clinic and/or ED and 60 children without asthma (controls) will be recruited from the ED. Recruitment will occur from May 2016 through November 2016.

Inclusion criteria for cases include asthma diagnosed by a clinician for greater than 1 year with a history of exacerbation requiring systemic corticosteroids within the past 2 years. Controls will have no history of asthma. All children, cases and controls, must (1) be in grade level 3-8 in the 2015-2016 school year, attend public school in Washington, DC (DCPS) and reside in their school district;(2) be accompanied by their parent or legal guardian. Exclusion criteria for cases and controls will be (1) presence of a chronic medical condition other than asthma or (2) a family that does not speak English or Spanish.

Demographic Data for Cases and Controls

Demographic information will be obtained by a structured interview; the questionnaire (Appendix A) will be used on both cases and controls: the parent/caregiver will be asked about the child's age, gender, race/ethnicity, insurance type. health care utilization, medications usage, highest level of education of the parent/ caregiver, income of the household, and parental report of school services. Cases will complete an additional 11 questions to determine asthma severity to determine NAEPP score and the Asthma Control Test (ACT) score (Appendix F and G).

We will utilize the child's electronic medical record (Cerner for ED charts and eClinicalWorks for the IMPACT DC charts) to determine insurance type and health care utilization. We will also determine each participant's weight and height from the medical record and will access medical records for the period of time we are collecting report cards for to determine clinical information, such as number of ED visits and hospitalizations over the 14 month period that the report cards cover (August 2015-November 2016).

Reporting of Academic Achievement and School Attendance

At the time of recruitment, families will be given a self-addressed, stamped envelope to send the child's 2013 first term (if available), standardized test score report (if available), and final report card to the research team. All report cards/score reports will be returned to the family via US Mail. Academic achievement, standardized test scores, and school attendance will be recorded from the report cards. All report cards in the DCPS system use the same grading scale..

The Self-Perception Profile

The self-perception profile is a reliable validated 6 question questionnaire for children in grades 6-8 that allows a child to self-evaluate their feelings about their engagement in school and their own school performance.

Reporting of the Quality of Life using the Peds QL 4.0 Form

QOL will be measured using the validated PedsQL 4.0 for children, teens, and parents (Appendices B, C, D, and E). The PedsQL 4.0 has four scales with 23 questions which ascertain physical functioning, emotional functioning, social functioning, and school functioning. A 5-point Likert scale is used in the child self-report and for the parent proxy reports. Items are reverse scored and linearly transformed to a 0 to 100 scale (0=100, 1=75, 2=50, 3=25, and 4=0), so higher scores indicate better QOL.

E. Statistical analysis Descriptive statistics will be used to analyze demographic variables (rates, proportions, means, medians, ranges). Univariate comparisons will be performed using appropriate categorical or continuous statistical analyses. Multivariate testing will be performed using logistic and/or liner regression where appropriate.

Sample Size: The study will be powered on the proportion of patients in each group with a grade point average >3.0. The overall proportion of DC public middle school students in the 2012-2013 school year with a GPA >3.0 was approximately 35%. Assuming that this figure is similar for children without asthma (controls), we will need 70 cases and 70 controls to have 80% power detect a 20% absolute difference in the proportion of children with asthma (cases) with a grade point average >3.0 (alpha = 0.05, two-sided).

We have chosen to include 120 children in the expansion of this original study, as we expect that less than 50% of all included patients will return their final year report cards via the self-addressed, stamped envelope.

F. Human Subjects

A convenience sample of potential participants' guardians will be approached in the temporal sequence that they are available either in the emergency department or in the IMPACT DC Asthma Clinic, informed about the research study, and invited to participate. Informed consent will be obtained from all guardians.

After obtaining informed consent, trained research assistants and/or the investigators will use extant hospital electronic data and information obtained from questionnaires as the source of research material for this study.

1. The risks of this study include inadvertent disclosure of protected health information. This risk does not exceed the daily risk of inadvertent disclosure of patients' protected health information during ED operations where patients' records are accessed through the ED tracking system of Logicare and the electronic medical records of EPRS.
2. There is the risk of feeling uncomfortable during the questionnaires; families will be told that some of the questions may make them uncomfortable and they are welcome to leave the study at any time, without penalty, if they feel uncomfortable. Alternatively, they may choose to leave questions unanswered.
3. There are no direct benefits to study participants. However, the knowledge gained from this study may allow us to identify a cohort of patients at special risk, for whom a targeted intervention would be appropriate.

4. Therefore, the risks are reasonable in relation to the benefits.

G. Risks and Side Effects

Questionnaires

Participants may find some of the questionnaires too personal; they will be offered the opportunity to refuse to answer any questions that make them feel uncomfortable. There is also the risk of breach of confidentiality; all participants will be assigned a random study number. This study number will be used to identify all questionnaires. Coding for the study numbers will be secured on a password protected file on the PI's hospital-issued laptop and stored on the secure CNMC server. We will store the study data in locked cabinets or offices.

H. Benefits

There are no direct benefits to participants.

I. Outside Consultants/Collaborators

None.

J. Contractual Agreements

None.

K. Costs To Subjects:

There is no cost to subjects.

L. Conflicts Of Interest:

There are no conflicts of interest.

M. Confidentiality:

The investigators will use reasonable measures to assure the security of these data, including locked office doors and file cabinets where paper records are stored, and secure, password-protected, computer software systems where electronic data are stored. The major risks to patients are the risks to confidentiality by inadvertent disclosure of protected health information. All paper data will be kept in the PI's locked office in locked file cabinets, to which only the PI will have keys for. All protected health information will be secured in password protected databases on the hospital Emergency Medical and Trauma Center (EMTC) drive. All research data will be de-identified and coded to further protect patient confidentiality. Code numbers and their respective medical record numbers will be kept in a separate password-protected database on the hospital's EMTC server. Passwords will only be known to the PI. These risks are reasonable in relation to the future anticipated benefits, which include identifying a future cohort of patients who might benefit from targeted interventions. The risk of inadvertent disclosure of protected health information is no more than minimal and no more than encountered on any patient visit to the ED.

N. Subject Compensation:

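### Report-card collection shares its end point with recruitment and has no stated return period for the last children enrolled, so obtainable GPAs could be lost

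*Combined protocol and SAP*

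**What the plan says.** All references are to the combined protocol and SAP.

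- **Section A, Specific Aim 1**, on the outcome data: "Report cards will be collected between May 2016-November 2016 or until 60 cases and 60 controls have been recruited".
- **Section D, Research Design and Methods**, on enrolment: "Recruitment will occur from May 2016 through November 2016".
- **Section D, Reporting of Academic Achievement and School Attendance**, on how cards arrive: "At the time of recruitment, families will be given a self-addressed, stamped envelope". The family posts the card later, and no deadline is given.
- **Section E, Sample Size**, on the number required: "we will need 70 cases and 70 controls". This is for 80% power to detect a 20-point absolute difference in the proportion with a GPA above 3.0, from 35% in controls ("alpha = 0.05, two-sided").
- **Section E, Sample Size**, on returns: "we expect that less than 50% of all included patients will return their final year report cards". The expansion enrols 120 children.

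No section gives a return period after the last enrolment, a closing date for receiving cards, or a rule for cards that arrive late.

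**The concern.** GPA comes from the report card, and the card reaches the investigators by post some time after the child is enrolled. Aim 1 nevertheless describes the end of card collection in terms of recruitment: the same calendar window, or the moment when the enrolment target is met. Neither limit refers to cards received.

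A data manager who followed the sentence literally could close the outcome file with cards still to come from the most recent enrolees. The sample size is a requirement for children with a GPA, and returns are already expected to be poor, so any avoidable loss matters. The loss would fall on children recruited last. It would differ between groups if cases and controls filled at different times.

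**Working it through.** **1. What each reading gives the last enrolee.** The sentence joins two limits with a bare 'or until' and does not say which governs.

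| Reading of Aim 1 | When collection ends | Time left for the last enrolee |
|---|---|---|
| Earlier of the two limits | Target met, or end of November 2016, whichever is first | None |
| Later of the two limits | End of November 2016, or later if the target is not yet met | None if recruitment fills the window or overruns it; the remainder of the window if the target is met early |
| Recruitment stop worded as collection | Not stated | Undefined |

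No reading assures a return period. The first can remove it, the second leaves it to the pace of accrual, and the third leaves the outcome with no closing point.

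**2. Reproducing the plan's 70 per group.** Inputs from Section E: p1 = 0.35, difference d = 0.20, two-sided alpha 0.05, power 80%. The hypothesis is worse performance in asthma, so p2 = 0.15. With the unpooled normal formula:

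n = (1.960 + 0.842)² × (0.35×0.65 + 0.15×0.85) / 0.20² = 7.849 × 0.355 / 0.04 = 69.66, so 70 per group.

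The stated figure reproduces. The opposite direction (35% v 55%) needs 94 by the same formula, so 35% v 15% is the intended contrast.

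**3. GPAs expected from the expansion.** Enrolment is 60 per group and return is below 50%: 60 × 0.50 = 30, so fewer than 30 per group if returns are balanced between cases and controls. Reaching 70 per group at 50% return would take 70 / 0.50 = 140 enrolled per group.

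**4. Power at those counts, 35% v 15%.** The normal approximation with pooled variance under the null is

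power = Φ{ [d√n − 1.960 √(2 × 0.25 × 0.75)] / √0.355 }, where 0.25 is the mean of the two proportions.

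At n = 30: (0.20 × 5.477 − 1.200) / 0.596 = −0.176, which gives 43.0%.

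| GPAs per group | Normal approximation | Exact enumeration, uncorrected chi-square |
|---|---|---|
| 70 | 78.6% | 79.7% |
| 60 | 72.1% | 73.5% |
| 30 | 43.0% | 43.5% |

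At 30 per group, the drop from 35% detectable with 80% power is about 29 points, not 20.

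**5. Any further loss from the collection wording.** The documents give no accrual rate, return delay or closing practice, so this has no derivable value. As an illustration only, suppose an assumed share of the 30 returned cards per group is lost:

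| Assumed loss | GPAs per group | Power (normal approximation) |
|---|---|---|
| 0% | 30 | 43% |
| 5% | 28.5 | 41% |
| 10% | 27 | 39% |
| 20% | 24 | 36% |
| 30% | 21 | 32% |

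The under-50% return figure does not say whether late cards are already counted as missing, so even this range may double count.

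**The case against.** The strongest reply is that the sentence is loosely written and nothing would actually be lost. Several places support this.

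- Aim 1 does not say that the earlier limit applies.
- Section D gives the identical window for recruitment, which suggests that a recruitment stop was described as collection.
- The Demographic Data part of Section D treats the cards as covering August 2015 to November 2016. That sits badly with closing collection months before November.
- Every family receives an envelope, including the last, and the conversation guide in Appendix H sets no deadline for return.

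This stands as far as it goes. A reader might infer that collection is set to stop early and that late cards are discarded. The documents do not support that, because no section refuses or excludes a late card. A reader might also infer that some 2015-2016 final cards would not yet exist at closure, or that the loss would differ between groups. Both depend on the earlier-limit reading and on accrual patterns that the plan does not give.

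The reply does not remove the gap. If the sentence is really a recruitment stop, the plan has no closing rule for its outcome data at all, and the same correction is needed.

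**Conclusion.** The point holds as a defect of specification. The end of card collection is worded as a recruitment milestone, cards arrive after enrolment, and the last enrolees have no assured return period. GPAs could be lost, by an amount that the documents do not allow anyone to derive.

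A reader might attribute the fall in power from about 80% to about 43% to this wording. That would be wrong. The fall comes from enrolling 60 per group with under 50% return, and it remains in full if the collection sentence is corrected. It assumes balanced returns and 35% v 15%.

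Nor is 43% established as the power of the whole study. Aim 1 calls the 60 cases additional, and Section E calls the 120 children an expansion of an original study whose number of GPAs is not given. That cohort would have to supply more than 70 − 30 = 40 GPAs per group to reach 70.

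**What to change.** Replace the Aim 1 sentence with two separate rules:

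- Recruitment stops at 60 cases and 60 controls.
- Report cards are accepted for every enrolled child until a fixed date after the last enrolment, for example 3 months.

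Define the evaluable number as returned 2015-2016 final report cards, counted by group. If collection has already finished, report the closing date actually used, how late cards were handled, and the returns by group.

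As a separate correction to Section E, restate power at the expected evaluable count, and give the number of GPAs by group that the original cohort contributes, if any.

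The cost is protocol wording and a later data lock. The collection change needs no additional children. The restated power will be less favourable than 80% unless the original cohort makes up the difference.

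### Aim 1 compares GPAs, the only powered comparison is the share with GPA above 3.0, and the plan does not say which one decides.

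*Combined protocol and SAP*

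**What the plan says.** Specific Aim 1 is: "To determine the association between asthma and school performance by comparing grade point averages (GPA) in children from 3rd-8th grade with and without asthma". It gives no threshold, and its stated expectation is directional: "We expect children with asthma will have lower GPAs".

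The Sample Size paragraph of Section E uses a different form of the outcome: "The study will be powered on the proportion of patients in each group with a grade point average >3.0". It takes 35% for controls, a 20-point absolute difference, 80% power and two-sided alpha 0.05, and arrives at 70 cases and 70 controls. The 3.0 cut-off appears nowhere else in the document.

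The analysis text leaves both forms open. The Abstract says: "We will use multivariable linear and logistic regression to determine if the presence of asthma is associated with school performance". Section E says: "Multivariate testing will be performed using logistic and/or liner regression where appropriate". No section names a primary outcome, a primary model or the covariates, although Section A states that "academic performance is dependent on many other factors, such as socio-economic status of the local district and resources available". The interview described in Section D collects "highest level of education of the parent/ caregiver, income of the household, and parental report of school services", and Appendix A records grade level. On comparability of GPA, Section D states: "All report cards in the DCPS system use the same grading scale".

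**The concern.** GPA can enter the analysis as a number or as above/not above 3.0, and the document supports each form in a different place. The phrase on choosing the regression where appropriate may only mean matching the model to the outcome type. That does not settle the matter, because GPA is used in both types.

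If the split decides, a child who moves from 2.9 to 2.0 contributes nothing to the comparison, and power may be lost. If GPA itself decides, the study has no stated power for its main comparison. If the choice is left until the results are known, a reader cannot tell whether the reported test was the planned one. The numbers make this matter: Section E expects fewer than half of families to return the final report card. The 60 per group in the expansion may then yield 30 per group or fewer, and at that size the two analyses have quite different power.

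**Working it through.** **1. The plan's own figure.** Inputs from Section E: p1 = 0.35, p2 = 0.35 − 0.20 = 0.15 (the hypothesised direction), two-sided alpha 0.05, power 0.80, equal groups.

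n = (p1q1 + p2q2)(1.960 + 0.842)² / d² = (0.2275 + 0.1275) × 7.849 / 0.04 = 69.66, rounded up to **70**. The stated figure is reproduced.

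**2. Power of the split at n per group.** Unpooled: Φ(0.20/√(0.355/n) − 1.960). Pooled: Φ((0.20 − 1.960√(0.375/n))/√(0.355/n)), where 0.375 = 2 × 0.25 × 0.75. Pooled/unpooled results are 43.0%/45.2% at 30, 72.1%/73.9% at 60 and 78.6%/80.2% at 70.

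**3. Power of continuous GPA for the same 35% v 15%.** Assumptions (not in the documents): GPA is normal, control SD = 1, case SD = r. Holding the two proportions fixed, the mean shift is r × z(0.85) − z(0.65) = 1.036r − 0.385. Power is from a two-sided Welch t-test with noncentrality shift/√((1 + r²)/n).

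| r (case SD / control SD) | Shift, control SDs | n per group for 80% | Power at 30 | at 60 | at 70 |
|---|---|---|---|---|---|
| 0.70 | 0.340 | 103 | 32% | 57% | 64% |
| 0.75 | 0.392 | 81 | 39% | 67% | 74% |
| 0.80 | 0.444 | 67 | 46% | 76% | 82% |
| 0.90 | 0.547 | 49 | 59% | 88% | 92% |
| 1.00 | 0.651 | 39 | 70% | 94% | 97% |
| 1.25 | 0.910 | 26 | 86% | 99% | 99.7% |
| Split at 3.0 (step 2) | – | 70 | 43–45% | 72–74% | 79–80% |

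The two analyses break even at r of about 0.78–0.79. Below that the split has more power.

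**4. Sensitivity to shape** (simulation, 0–4 scale assumed). With left-skewed GPA (control skew about −0.4, SD ratio 1.02–1.05), continuous v split is 96% v 80% at 70 and 67–68% v 44% at 30. With normal GPA capped at 4.0 (2–11% of controls at the cap), it is 97% v 80% and 69–70% v 43–44%. Skewness and a ceiling of this size do not change the comparison; the SD ratio does.

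**5. If either test could count.** With no true difference, normal GPA and each test at 0.05, the simulated chance that at least one is significant is 7.7%, 8.0% and 7.8% at 30, 60 and 70 per group. For independent tests it would be 1 − 0.95² = 9.75%.

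**6. Detectable difference for continuous GPA** (80% power, unadjusted, equal SDs): 0.74 SD at 30 per group and 0.52 SD at 60. For assumed SDs of 0.6, 0.8 and 1.0 GPA points, these are 0.44, 0.59 and 0.74 points at 30, and 0.31, 0.41 and 0.52 at 60.

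**The case against.** The best defence is that a comparison of the share above 3.0 is a comparison of GPAs. Aim 1 never says mean or continuous, a lower share fits the expected direction, and the split is the only comparison with a control rate, an effect size and a power. On that reading the split is the main analysis and only a label is missing. Much of this stands. A reader might infer that the split fails to answer Aim 1, or that 70 per group is wrong; the documents support neither. What remains is that the label is absent and that, if the split decides, information on either side of 3.0 goes unused.

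A second defence is that preferring continuous GPA rests on an SD the documents do not give. That is correct. The gain is conditional on the SD ratio and reverses below about 0.78.

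A third is that a fully adjusted model could do harm at small n. This also stands. With 30 per group and grade, education and income all entered as categories (about 25 parameters), simulation gave about 14–15% false positives for an HC0 robust test with a normal cut-off. HC1 with a t cut-off held at about 5%, and linear coding of the covariates avoided the problem. The model therefore has to be specified.

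Finally, the document is dated June 2018 and report cards were to be collected in 2016. Changing the deciding outcome after seeing GPA data would add the very flexibility at issue.

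**Conclusion.** The concern holds in limited form. Aim 1 and the sample size use different forms of GPA, and nothing says which decides. The 70 per group is right for the split. If the split decides, it costs roughly 17 points of power at 70 per group (79–80% v 97%) and about 25 at 30 (43–45% v 70%), provided GPA is roughly normal with similar SDs in the two groups. There is no such cost if cases are much less spread out than controls. The 30-per-group figures describe the expansion alone at a 50% return; the document does not say how many original-study participants would be added.

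A reader might also infer that the plan runs at an 8% false-positive rate. It does not say so. That figure applies only if either unadjusted test were allowed to count, which no section states.

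This should be corrected. It does not invalidate the design.

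**What to change.** State in Section E that continuous GPA from the final report card is the primary outcome for Aim 1. Use the same report-card definition for every participant counted, including any from the original study; this needs saying because Section D asks for a 2013 first-term card while eligibility is set by the 2015–2016 year.

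Analyse it by one linear regression on asthma status with few parameters: grade level, parental education and household income, as linear scores or a few collapsed groups. Give a rule for the Refused and Don't know income responses in Appendix A. Use small-sample robust standard errors, for example HC1 with a t reference.

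Keep GPA above 3.0 as secondary and label the 70-per-group calculation as belonging to it. State the unadjusted detectable mean difference at the number of report cards expected (step 6), with the SD declared as an assumption.

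If GPA data had already been examined when the choice is made, keep GPA above 3.0, the only powered comparison, as the deciding analysis and report the continuous analysis as post hoc.

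Cost: nothing new is needed from families. An SD must be assumed, since the only benchmark given is the 35%. A mean difference is harder to read than a percentage, so both should be reported. Power is lower than for the split if the case SD is below about 0.78 of the control SD.
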